Myelomeningocele (MMC) is one of the most serious congenital defects with an incidence of 0.3 to 4.5 per 1000 births [1]. This defect is caused by the inability of neural tube to close during early gestational period and usually presents by lower limb paresis and bowel and bladder dysfunction [2]. Bladder dysfunction caused by disordered innervation of detrusor muscle and external urethral sphincter that may lead to hydronephrosis or reflux and finally renal failure with life-threatening conse-

quences [3]. Treatment of urinary system dysfunction is primarily aimed at preventing upper urinary tract damage and secondarily at gaining continence and improving quality of life and social interactions [4]. Initial treatment is based on clean intermittent catheterization (CIC) and anticholinergic medications. In those who fail to respond to medical treatment, surgical procedures might be needed [5].

Neurogenic bladder is defined as dysfunction of the bladder resulting from damage to or disease of the central nervous system (CNS) [6], and thus is a broad diagnosis, as it describes bladder dysfunction resulting from any neurological insult to the CNS [7]. Neurogenic bladder dysfunction (NBD) is present in all patients with spinal cord injury (SCI) with persistent neurological deficits and in 70% of ambulatory patients with SCI [8]. It is also common in spina bifida, which affects about one in every 1000 live births [9]. The commonest cause of NBD is myelomeningocele. Other causes of NBD involving the spinal cord include, spina bifida occulta, lipomeningocele, sacral agenesis, and tethered spinal cord associated with imperforated anus, and cloacal malformations [10, 11, 12, and 13].

Magnetic field stimulation (MFS) is non-invasive technique with low side effect risks and without problems of drug interactions in chronic inflammatory diseases [14], it stimulates the nervous system and can activate deep neural structures by induced electric currents, without discomfort or pain [15]. Pulsating electromagnetic field (PEMF) stimulation showed anti-inflammatory effects in Crohn's disease patients by induction of peripheral blood mononuclear cells apoptosis and changes in cytokine profile [16].

Subjects and methods:

A pretest-posttest randomized controlled study was conducted in outpatient clinic in faculty of physical therapy, Cairo University. Informed consent was provided for each child from their parents. The procedures followed were in accordance with the Institutional Ethical Committee Clearance No: P.T.REC/012/002423.

Subjects:

Forty myelomeningocele children with neurogenic bladder were enrolled in this study and were assessed for eligibility. Their ages ranged from four and twelve years (15 girls and 25 boys). The children participated in this study were from both sexes, with stable medical and psychological status, had the same socioeconomic status, able to follow the verbal commands or instructions. We excluded children with visual or auditory problems, children with any neurological manifestation rather than spina bifida, medically unstable children especially with cardiovascular disorders, or mentally retarded children, children with any sign of urinary tract infection, or any implanted metal and uncooperative children.

They were assigned randomly into two equal groups. Group (A) the control group received medical care and standard urotherapy only. And group (B) the study group received the same medical care and standard urotherapy in addition to pulsed electromagnetic field therapy. PEMFT applied at sacral area for 20 min (5 Hz, with a 15% intensity output for 5 s/min), three times / week for three successful months. All children were assisted using urodynamic studies before and after three months of intervention.

Materials for evaluation:

The children were selected and diagnosed by urologist and neurologist as having neurogenic OAB dysfunction based on careful neurological and urological investigations including patient history, physical examination, urine analysis, and Urodynamic studies (UDS).

UDS is objective way to evaluate urinary functioning and includes: urinary flowmetry, bladder cystometrogram/electromyogram, and urethral pressure profiling and valsalva leak-point pressure measurement. The most definitive way to determine urethral functioning and abnormalities in bladder in the filling/storage phase, as well as neurogenic bladder dysfunction in the voiding phase [17].

All children were assisted using UDS pre and post treatment period that included: maximum urinary flow rate (Qmax), maximum cystometric capacity (MCC) and first uninhibited detrusor contraction to measure bladder capacity, detrusor pressure at Qmax, and compliance.

Flow chart

[figure not shown]

Fig 1, flow chart

Methods of Treatment

- Group (A) the control group received medical care and standard urotherapy only.
- Group (B) received the same medical care and standard urotherapy in addition to pulsed electromagnetic field therapy. The children were instructed to laying in prone position and PEMFT applied at sacral area for 20 min (5 Hz, with a 15% intensity output for 5 s/min), three times / week for three successful months. All children were assisted usingurodynamic studies before and after three months of intervention.

Statistical analysis

For analysis of data in the present study, SPSS software version 21 was used for data analysis. Descriptive statistics was used to identify the mean and standard deviation for each variable. Paired t-test was used to test pre and post changes in each group of the study.

References:

4. Nijman RJ: Neurogenic and non-neurogenic bladder dysfunction. *CurrOpinUrol*; 11: 577-83, (2001).
5. Kajbafzadeh AM, Chubak N: Simultaneous Malone antegrade continent enema and Mitrofanoff principle using the divided appendix: report of a new technique for prevention of stoma complications. *J Urol*; 165: 2404-9, (2001).
6. Al-Shukri S.A. Neurogenic bladder – assessment, investigation, and treatment. *EurUrol Rev*; 7:55–60, (2012).
7. Newman DK. Managing Urinary Retention in the Acute Care Setting. IJsselstein, the Netherlands; Verathon Medical (Europe), 2011. Available at: <http://cardiogenicsltd.com/system/files/341/original/managing-urinary-retention.pdf?1463046777>. Accessed February (2017).

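### Bladder volumes are tested pre to post only within each arm, with no allowance for age and no between-arm test, so three-month growth cannot be separated from treatment.

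*Combined protocol and SAP*

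**What the plan says.** Under Subjects, the document states that "Forty myelomeningocele children with neurogenic bladder were enrolled in this study", gives the age span as "Their ages ranged from four and twelve years (15 girls and 25 boys", and says of allocation that "They were assigned randomly into two equal groups". That makes 20 children per arm. Age is not mentioned as a stratification factor.

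Under Materials for evaluation, the urodynamic outcomes are "maximum urinary flow rate (Qmax), maximum cystometric capacity (MCC) and first uninhibited detrusor contraction to measure bladder capacity, detrusor pressure at Qmax, and compliance". Two of these, MCC and the volume at first uninhibited contraction, are bladder volumes. On timing, Subjects says "All children were assisted using urodynamic studies before and after three months of intervention".

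The Statistical analysis section has one descriptive step, "Descriptive statistics was used to identify the mean and standard deviation for each variable", and one test, "Paired t-test was used to test pre and post changes in each group of the study". Nothing there or elsewhere describes scaling to age or body size, an age covariate, or a comparison of the two arms. The Abstract draws its efficacy conclusion from increases that reached significance in the study group alone.

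The document does not state the unit of the volumes. That they are analysed as plain mL is inferred from the absence of any scaling step.

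**The concern.** Bladder capacity rises with age across 4 to 12 years. This raises two separate issues.

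- **Growth.** Every child is three months older at the second study. A paired test within the study arm estimates treatment plus growth plus anything else that changes over three months, including any effect of the urotherapy that both arms receive. Randomisation provides a control arm to subtract this common change, but the planned analysis never makes the subtraction. Finding significance in one arm and not in the other is not a test of the difference between them.
- **Size.** The same gain in mL is a large relative change in a small bladder and a modest one in a large bladder. A single mean gain over this age range is therefore hard to read clinically, and the spread in size may add variance.

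The first issue can lead to a wrong efficacy conclusion. The second affects interpretation and precision.

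**Working it through.** The plan has no power, SD or effect-size figure to reproduce, so the check is of consequences.

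**Inputs from the document:** ages 4 to 12; 40 children in two equal arms, so n = 20 per arm; three months between studies; paired t-test within each arm. The 0.05 level appears only with the results in the Abstract; two-sided testing is assumed.

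**Assumptions (not in the document):** ages uniform on 4 to 12; expected capacity either 30 × (age + 1) mL (steep) or 20 × age + 90 mL (flat); SD of the three-month change between 15 and 60 mL.

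**1. Growth.** Steep: 30 mL/year × 0.25 year = 7.5 mL. Flat: 20 × 0.25 = 5 mL.

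**2. Planned test with no treatment effect.** The noncentrality is drift / SD × √20, with 19 degrees of freedom. For example, 7.5 / 15 × √20 = 2.24. Two-sided rejection rates:

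| SD of change (mL) | 5 mL drift | 7.5 mL drift |
|---|---|---|
| 15 | 29% | 56% |
| 20 | 19% | 36% |
| 30 | 11% | 19% |
| 40 | 8% | 13% |
| 60 | 6% | 8% |

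**3. Significant increase in the study arm only.** With equal drift in both arms and no treatment effect, the probability is P(significant increase in one arm) × P(not significant in the other). At 7.5 mL drift it is about 25% (SD 15) to 7% (SD 60). With no drift it is 0.025 × 0.95 = 2.4%.

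**4. Between-arm test on the same data.** With 7.5 mL drift in both arms, a two-sample t-test on raw change rejected in 5.3% (SD 20) and 5.1% (SD 40) of 20,000 simulated null trials. The drift cancels without any age scaling.

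**5. Size and interpretation.** Expected capacity runs from 150 to 390 mL (steep, a ratio of 2.6) or 170 to 330 mL (flat, 1.9). A 40 mL gain is 40/150 = 27% of expected at age 4 and 40/390 = 10% at age 12 (flat: 24% and 12%).

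**6. Size and variance.** The SD of age is 8/√12 = 2.31 years, so the SD of expected capacity is 30 × 2.31 = 69 mL (flat: 46 mL). If the gain were 20% of expected capacity, size would contribute 0.20 × 69 = 14 mL to the SD of change. An SD of 20 becomes √(20² + 14²) ≈ 24, and an SD of 40 becomes about 42.

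**7. Chance age imbalance.** For unadjusted post-treatment means, the SE is 69 × √(2/20) = 22 mL (flat: 15 mL). For changes proportional to capacity (10% to 30%), it is 0.10 × 22 = 2.2 to 0.30 × 22 = 6.6 mL (flat: 1.5 to 4.4 mL).

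**8. Would scaling to age help precision?** The measure is the squared ratio of standardised mean change, scaled against raw. If the gain is proportional to capacity (mean 10% to 30%, SD 15% to 20%), it is 1.09 to 1.33 (steep) or 1.05 to 1.17 (flat). If the gain is a fixed number of mL unrelated to age (mean 20 to 60 mL, SD 30 to 60 mL), it is about 0.72 to 0.91 (steep) or 0.84 to 0.96 (flat). The direction depends on a response pattern that the document does not establish.

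**The case against.** The strongest reply is that each child is compared with their own baseline, so differences in size cancel from the change. This stands. A reader might infer that the measured change is biased because it mixes child size with treatment; the paired design does not support that.

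A second reply is that growth over three months is small and acts on both randomised arms alike. Both parts are true. The second would be decisive if the arms were compared, but Statistical analysis contains no such comparison. The first does not rescue the within-arm test unless the SD of change is large.

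A third reply concerns chance imbalance in age. A reader might take the 22 mL SE, about ±43 mL at 95%, as the error in the trial's result. It applies to an unadjusted comparison of post-treatment means, which is not planned. On the change the SE is about 1.5 to 6.6 mL, and only if response is proportional to capacity.

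Finally, every capacity figure here is assumed. The document gives no capacity-for-age formula, growth rate, age distribution or SD, and does not show that children with neurogenic bladder follow a normal growth curve. This also stands. It is why the results are given as ranges, and why percentage of expected capacity is not put forward as the main outcome.

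**Conclusion.** The point holds in this form: the planned within-arm tests cannot separate three months of growth from treatment, and no between-arm test is planned that would do so. At an assumed 7.5 mL of growth and no treatment effect, the test rejects in about 8% to 56% of trials for an SD of change from 60 down to 15 mL; at 5 mL it rejects in about 6% to 29%. The size of the problem rests on those assumed values. That the test does not isolate treatment rests only on the design.

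The lack of any allowance for age is a secondary matter of variance and interpretation. Two further inferences are not supported. Capacity does not differ severalfold on these formulas; the ratio is 1.9 to 2.6. Nor does the check show that the increases reported in the Abstract were caused by growth. It shows only that the planned analysis could not tell.

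**What to change.** In Statistical analysis, base the efficacy conclusion for MCC and volume at first uninhibited contraction on a between-arm ANCOVA: post-treatment volume as outcome, arm as factor, baseline volume and baseline age as covariates. Report the arm difference with its confidence interval. Keep the within-arm changes as descriptive results only.

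As a supporting table, not the main outcome, show pre and post volumes as a percentage of age-expected capacity, using one stated formula and the child's age at each study. This gives the reader a scale that is comparable across ages.

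The cost is one or two degrees of freedom and a little analysis work. Ages and volumes are already collected, so no visit, procedure or child is added. In simulation the adjustment cost about 1 to 3 percentage points of power at worst, and gained about 3 when baseline volume was measured with error. The percentage table depends on the formula chosen, and that scale is less efficient than mL if the gain is unrelated to bladder size. Since the Abstract already reports results, the revised analysis should be labelled as specified after them.
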